3.2. Per Protocol Population

A per-protocol analysis population will be defined as those subjects that are part of the Primary Analysis Population, have worn the Jewel on average for at least 14.1 hours a day, and are without major protocol deviations which may affect the primary safety or effectiveness endpoint measurements. Analyses on the safety and effectiveness endpoints will be repeated on this population.

3.3.Safety Analysis Population

The safety analysis population will consist of all subjects who remain enrolled for longer than 12 hours after the date and time the first Jewel applied to the subject's body transitions to Monitor Mode, regardless of analyzable wear time. For example, if a subject wore the Jewel and subsequently does not return the device or the device was damaged, this subject is still part of the safety analysis population and will be assessed for clinically significant cutaneous Adverse Device Effects.

4. Study Objectives

4.1. Primary Effectiveness

The primary effectiveness endpoint is to demonstrate an observed inappropriate shock rate of no more than 2.0 inappropriate shocks per 100 patient-months using a one-sided upper 98% confidence interval at the final analysis.

4.2. Secondary Effectiveness

The first secondary effectiveness endpoint is to observe successful conversion of at least one shockable rhythm with a salvo of up to five (5) shocks. If multiple successful conversions occur in a single subject, conversions will be counted as separate events only if the rhythm returned to a non-shockable rhythm between conversions (i.e., the Jewel returns to Monitor Mode).

The second secondary effectiveness endpoint is to observe a compliance rate of subjects wearing the Jewel of greater than 14.1 average hours per day during a prescription wear period.

4.3. Primary Safety

The primary safety endpoint is to observe a rate of subjects experiencing clinically significant cutaneous Adverse Device Effects of <15%.

5. Study Endpoints and Analysis

5.1. Primary Effectiveness Endpoints

All shocks during analyzable wear time will be recorded, centrally evaluated and adjudicated by the Clinical Events Committee (CEC), and reported.

The primary effectiveness endpoint is the rate of inappropriate shock. A one-sided upper 98% confidence limit will be calculated for the inappropriate shock rate per 100 patient-months at the final analysis. Specifically, an intercept-only Poisson regression model will be fit to the data. All wear times through the first inappropriate shock or through death or withdrawal or wear times for subjects without inappropriate shock, death, or withdrawal at the time of analysis will contribute to the Poisson regression model. The one-sided upper 98% confidence limit inappropriate shock rate will be calculated by taking the one-sided upper 98% confidence limit of the intercept parameter in the regression model. The null hypothesis will be rejected if the upper confidence limit on the inappropriate shock rate is less than 2.0.

The formal hypotheses are:

 H_0 : Inappropriate shock rate ≥ 2.0 per 100 patient-months H_a : Inappropriate shock rate < 2.0 per 100 patient-months

The analysis will be re-run on the per protocol analysis population if that population is different from the primary analysis population. Results of this analysis are strictly supportive.

Note that subjects experiencing an inappropriate shock will continue to be followed and accumulate wear time in order to collect data on the other endpoints of this trial.

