3.2 Endpoints

3.2.1 Primary Effectiveness Endpoint

To demonstrate an observed inappropriate shock rate of no more than 2.0 inappropriate shocks per 100 patient-months using a one-sided upper 97% confidence interval and >83% power at the interim analysis; and a 98% confidence interval and >98% power for the final analysis.

An inappropriate shock is defined as a shock delivered during a period where the study subject is not experiencing life threatening VT or VF. Only first inappropriate shocks will contribute the analysis of this endpoint. All inappropriate shocks will be reviewed and adjudicated by a Clinical Events Committee (CEC) and reported throughout the prescription period.

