5.5. Interim Analyses

An interim analysis of the Primary Endpoints will be performed after 179 subjects or more have completed their prescription wear time. This analysis will be used to stop the trial early for both safety and effectiveness.

This interim analysis will be analyzed as described in Section 5.1 above, with the exception that a one-sided upper 97% confidence bound will be used. This effectively spends 0.03 alpha on the interim analysis, reserving 0.02 alpha for the final analysis. Splitting the overall alpha into two pieces that add up to the overall alpha is a recognized way of controlling the Type I error rate. This can be seen by calculating the probability of making a Type I error. First calculate the probability of not making a Type I error which is:

Prob(no Type I in interim analysis)*Prob(no Type I in final analysis)= 0.97*0.98=0.9506

The probability of making a Type I error is then one minus the probability of not making any Type I errors which is:

Prob(Type I error)= 1.0 - 0.9506 = 0.0494

This particular split in alpha also corresponds to using a cumulative error spending function of Jennison and Turnbull (2000) defined as:

$$E(t,\rho) = \begin{cases} 1 & if \quad t \ge 1 \\ t^{\rho} & if \ 0 < t < 1 \\ 0 & otherwise \end{cases}$$

where ρ is the power parameter (here ρ =1.059) and t is the information fraction at the time of the interim analysis (here t = 179/290). Given these values, the amount of alpha spent at the interim analysis is:

 $\alpha^* E(179/290, 1.059) = 0.05^*(179/290)^{1.059} = 0.02999$

The safety endpoint will also be tested at this interim analysis only if the primary effectiveness endpoint is achieved. The trial will only be stopped if both the primary effectiveness and primary safety endpoints are achieved.

There is another planned analysis when 100 subjects have completed their prescription wear time, which will be performed to support application for CE mark. The data will be summarized descriptively and no formal hypothesis testing will be done at this point, so no adjustment for Type I error rate is necessary. Once discussions with the Notified Body are concluded, this document will be updated with details regarding the analysis.

6. Handling of Missing Data

It is expected that most subjects will wear the device between 40 and 90 days. Subjects with missing wear times will not have their data imputed for the purpose of the primary endpoint analysis.

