7.2. Subject Accountability

Subject accountability will be presented in tabular form. This table will summarize how many subjects were screened and enrolled into this trial. This table will also summarize the number of subjects withdrawing from the study and the reason for withdrawal.

Screen failures are defined as subjects who consent to participate in the clinical trial, but who do not subsequently wear a Jewel (Jewel does not enter Monitor Mode). These subjects will not be included in any study analyses. A minimal set of screen failure information will be captured, including demographics, screen failure details, and eligibility criteria.

8. Sample Size Estimation

A Scientific Literature Review was performed to determine a clinically meaningful rate for inappropriate shocks and safety events. This is documented in the Report of Prior Investigations.

The estimated power for the primary effectiveness endpoint analysis is based off Monte-Carlo simulations. In order to assess power, 10,000 studies were simulated using various study sizes. For each subject within a study, a random wear time was assigned using a normal distribution with an average of 2.5-months and a standard deviation of 0.5 month. Each subject was also assigned a time to inappropriate shock using an exponential distribution. If the time to inappropriate shock is greater than the wear time, then that subject did not experience an event during the course of the trial. If the time to inappropriate shock is less than the wear time, then that subject is considered to have had an event. For subjects experiencing an event, wear time beyond the time to inappropriate shock is in not counted in the simulations. Since inappropriate shock is a rare event, some of the simulated studies had no subjects that experienced an inappropriate shock. When this happened, the study with zero total events was given a total of 0.5 events in order to allow for convergence of the models. Each study was then used to fit a Poisson regression model from which an estimated rate of inappropriate shock along with a one-sided 98% upper bound on that rate was generated. If

that upper bound was below the performance goal, then that study is considered successful, otherwise it is considered to have failed. Adding up the number of successful trials gives an estimate of power for a given sample size.

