The primary effectiveness endpoint of the rate of inappropriate shock will also be analyzed separately for males and females, COVID positive and COVID negative subjects, and for subjects whose BMI is >25 and those with BMI ≤25. Since these sub-groups are not powered, a formal analysis will not be done. Rather the rate of inappropriate shocks will be calculated and 95% two-tailed exact confidence intervals constructed about the rate will be given.

² Olgin JE. et al. Wearable Cardioverter-Defibrillator After Myocardial Infarction. NEJM 2018;379:1205-15

11. Additional Analyses

Jewel System Compliance

All additional analyses will be performed on the primary analysis population.

Subject compliance with using the Jewel will be evaluated using mean weekly wear, wear per device, and time between devices. Mean weekly wear will be measured every 7 days and time between devices will be measured in hours.

The number of hours a subject wears the Jewel during a particular week will be calculated for each subject over the duration of their prescription. The total time between devices will be subtracted from the total wear time, then be averaged for the number of weeks of wear within each subject to provide an average weekly wear time for that subject. The average weekly wear times will then be summarized across subjects using descriptive statistics.

Since each subject will use more than one device over their prescribed time, the time between a subject removing one Jewel and putting on another Jewel will be measured. The device syslog will timestamp transitions between Modes, enabling the calculation of removal time, application time and the time the device transitions the Monitor Mode. Upon availability of the mobile application in the study, the average number of hours for each subject during the transition from one Jewel to another will be calculated. Periods of removal time as attested to by a subject or health care provider and confirmed by electrocardiographic data will be included in the calculation of removal time. These transition times will be summarized across subjects using descriptive statistics.

These measures of compliance will be presented in table format.

Detection of Ventricular Arrhythmias

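### The primary effectiveness analysis has no rule for zero inappropriate shocks, an outcome with about a 19% chance at the interim look

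*SAP*

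**What the plan says.** SAP Section 5.1 specifies that "an intercept-only Poisson regression model will be fit to the data", counting only first inappropriate shocks and wear time up to them. The bound comes from that model: "The one-sided upper 98% confidence limit inappropriate shock rate will be calculated by taking the one-sided upper 98% confidence limit of the intercept parameter". The decision follows directly: "The null hypothesis will be rejected if the upper confidence limit on the inappropriate shock rate is less than 2.0". The type of limit (Wald, likelihood-ratio or exact) is not named.

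SAP Section 5.5 carries the method to the interim look: "This interim analysis will be analyzed as described in Section 5.1 above, with the exception that a one-sided upper 97% confidence bound will be used".

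Zero-event data appear only in SAP Section 8, which describes the power simulation. It notes: "Since inappropriate shock is a rare event, some of the simulated studies had no subjects that experienced an inappropriate shock". It then says how these were handled: "the study with zero total events was given a total of 0.5 events in order to allow for convergence of the models". Neither SAP Sections 5.1, 5.5 and 6 nor Protocol Section 9.1 carries this rule, or any other, into the analysis.

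Protocol Section 3.2.1 attaches these power figures to the endpoint: ">83% power at the interim analysis; and a 98% confidence interval and >98% power for the final analysis". Exact limits are already used elsewhere in the SAP. Section 5.3 uses Clopper-Pearson for primary safety, and Section 10 says of the shock rate in subgroups that "95% two-tailed exact confidence intervals constructed about the rate will be given".

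**The concern.** In an intercept-only Poisson model the intercept is the log of events divided by exposure. With zero events its estimate is minus infinity and its standard error is undefined, so a Wald upper limit cannot be computed. The analysis sections then give no answer for the result most favourable to the device, and someone would have to choose a method after seeing the data, in an unblinded single-arm trial that may stop at that look.

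Two further points follow. The stated power counts zero-event trials as successes under a rule the analysis sections do not contain. And because the type of limit is unnamed, other readings of the same sentence can lead to different decisions at non-zero counts.

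**Working it through.** **Inputs.** Rate 0.37 per 100 subject-months; wear time normal, mean 2.5 and SD 0.5 months; exponential time to first shock; goal 2.0 per 100 (SAP Sections 5.1 and 8). Interim: 179 subjects, 97% limit (SAP Section 5.5). Final: 290 subjects, 98% limit. Planned exposure: 179 × 2.5 = 447.5 and 290 × 2.5 = 725 patient-months.

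**Formulas**, with d = subjects with a first inappropriate shock and T = patient-months:
- Wald limit: 100 × (d/T) × exp(z/√d), with d = 0 replaced by 0.5 under the Section 8 rule.
- Exact limit: 100 × chi-square(conf, 2(d+1)) / (2T).

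**Step 1: the plan's power.** Simulating 200,000 trials as Section 8 describes, Wald with the 0.5 rule gives 83.7% at the interim and 98.1% at the final. This matches the stated figures.

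**Step 2: chance of zero events.** exp(−0.0037 × 447.5) = 19.1% and exp(−0.0037 × 725) = 6.8% (simulated 19.0% and 6.7%). The two overlap, since a trial with no events at the final also had none at the interim. If mean wear ran from 40 to 90 days, the range SAP Section 6 expects for most subjects, the chance would run from 42% to 14% at the interim and from 24% to 4% at the final.

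**Step 3: what the model returns.** A Poisson GLM fitted to 179 subjects with no events stopped with an error. With a supplied start value it gave an intercept of −26, a standard error of about 12,700 and an infinite upper limit. With one event it converged (limit 1.47).

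**Step 4: limits at 447.5 patient-months, 97%, per 100.**

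| d | Wald, 0.5 rule | Exact | Likelihood-ratio |
|---|---|---|---|
| 0 | 1.60 | 0.78 | 0.40 |
| 1 | 1.47 | 1.20 | 0.94 |
| 2 | 1.69 | 1.56 | 1.33 |
| 3 | 1.99 | 1.90 | 1.68 |

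For example, at d = 0: 0.5/447.5 × exp(1.881/√0.5) × 100 = 1.60, against −ln(0.03)/447.5 × 100 = 0.78. The 0.5 rule ranks zero shocks worse than one. At the final (725 patient-months, 98%), seven events give Wald 2.10 and exact 2.04 (both fail) but likelihood-ratio 1.92 (passes).

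**Step 5: operating characteristics** (effectiveness only; interim / final / either look).

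| Handling | Power at 0.37 | Type I error at 2.0 |
|---|---|---|
| Wald, 0.5 rule | 83.7% / 98.1% / 98.3% | 1.4% / 1.1% / 2.1% |
| Exact limit | 91.5% / 98.1% / 98.5% | 2.3% / 1.2% / 2.9% |
| Likelihood-ratio | not tabulated | 2.6% / 2.6% / 4.3% |
| Wald, if zero events gave no success | 64.7% / 91.3% / 91.6% | – |

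The last row is conditional, because the SAP does not say that zero events would fail. It shows how much of the power rests on the unwritten rule: 19.0/83.7 = 23% of interim successes and 6.7/98.1 = 7% of final ones.

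The interim gain from the exact limit comes from d = 3 (probability 14.4%). Three events pass under Wald only from 444 patient-months, and mean simulated exposure is 445, so they pass in 46% of trials. Under the exact limit they pass from 425 patient-months, in 99.7% of trials.

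**Step 6: when the zero-event choice changes the decision.** With d = 0 at the interim, the 0.5 rule passes only above 357 patient-months (357/179 = 2.0 months per subject) and the exact limit from 175 (1.0 month). At the final the thresholds are 456 and 196. If mean wear were 40 days (40/30.4 = 1.32 months, about 236 patient-months), zero interim events would give 3.03 under the 0.5 rule (fail) and 1.49 exact (pass).

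**The case against.** The strongest reply is that no decision depends on the gap at planned exposure. With zero events all three limits are far below 2.0, and every simulated zero-event trial passed at both looks. Section 8 also shows what the sponsor intended, and the stated power is reproduced with Wald and the 0.5 rule, so one sentence carried into Sections 5.1 and 5.5 would close the gap. Replacing the limit at every count goes further than the defect requires and eases early stopping. The 7% at the final has little practical weight, because such a trial would normally have met effectiveness at the interim already. The likelihood-ratio excess arises at non-zero counts and is a weak reading of the SAP, since it does not reproduce the stated power.

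Most of this stands as a limit on the consequence. It does not remove the gap: a simulation step adopted for convergence is not an analysis rule, and intent inferred from a power calculation is not pre-specification. The decision can also change if exposure falls short, within the range of wear the SAP itself expects. The easier interim bar is a real cost of the exact limit and should be stated openly. Error stays within the 3% and 2% allotted.

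**Conclusion.** The concern holds. As written, SAP Sections 5.1 and 5.5 give no decision for zero inappropriate shocks, an outcome with about a 19% chance at the interim and 7% at the final (overlapping) if the true rate is 0.37 per 100 patient-months and mean wear is 2.5 months. The stated power depends on an analysis rule that appears only in the simulation.

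The consequence is moderate. The gap does not inflate type I error, and the choice between the 0.5 rule and the exact limit barely changes success at either look (98.3% versus 98.5%). What it affects is pre-specification and the chance of an early stop. It should be fixed, and before interim data are seen.

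**What to change.** **Preferred.** In SAP Sections 5.1, 5.5 and 8, define the bound as the exact one-sided Poisson upper limit, chi-square(conf, 2(d+1)) / (2 × patient-months), scaled to 100 patient-months. Use conf = 0.97 at the interim and 0.98 at the final, for any d including zero. Keep the Poisson regression as supportive. Restate power as about 91-92% at the interim, 98% at the final and about 98.5% at either look, and align Protocol Section 3.2.1. This matches the exact methods already used in SAP Sections 5.3 and 10.

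**Minimum.** Name the Wald limit and state the 0.5-event rule in Sections 5.1 and 5.5. This preserves the stated power but ranks zero shocks worse than one. That reversal affects decisions only at 328-357 patient-months (interim) or 390-456 (final), below the planned exposure.

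**Cost.** SAP wording and a simulation re-run, with no extra patients. The exact limit lowers the interim bar: three events pass from 425 rather than 444 patient-months, zero events from 175 rather than 357, and interim type I error rises from 1.4% to 2.3%. The amendment should say so and be dated before any interim data are reviewed.

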5.2. Secondary Effectiveness Endpoints

The secondary endpoint of successful conversion of at least one shockable rhythm with a salvo of up to five (5) shocks will not be formally tested. A shock is considered appropriate if the shock is delivered during a period where the subject is experiencing VF or a VT that is considered "life threatening" (as adjudicated by the CEC). Each shockable episode of lifethreatening VT (as defined by the CEC) or VF encountered during the course of the trial will be described and the outcome of any conversion attempt documented. If multiple successful conversions occur in a single subject, all successful conversions will be included in the secondary endpoint analysis. The number and percentage of successful conversions will be given.

5.3. Primary Safety Endpoints

The statistical method used for testing the primary safety endpoint will use a one-sided, exact 95% upper confidence bound which will be compared to the performance goal of 15%. The exact confidence bound will be constructed using the Clopper-Pearson method. The hypotheses tested will be as follows:

 $H_0: \pi \ge 0.15 \\ H_a: \pi < 0.15$

where π is the observed proportion of subjects experiencing a clinically significant cutaneous adverse device event.

An ADE will be considered "clinically significant" if it results in the subject being permanently withdrawn from the clinical trial by the Investigator.

Additionally, all Adverse Device Effects and device-related Serious Adverse Events (SAE) will be tabulated and presented along with duration and severity. The proportion of subjects experiencing an ADE or SAE will also be presented. All device-related events will be reviewed by the Oversight Committee. All Adverse Device Effects and device-related SAEs will be tabulated and presented.

A summary of all AEs and SAEs, including the proportion of subjects experiencing an AE or SAE, along with duration, severity, and relatedness to the Jewel will also be presented to ensure that device safety performance is adequately summarized.

5.4. Secondary Endpoint

The secondary endpoint is to observe a compliance rate of subjects wearing the Jewel of greater than 14.1 average hours per day during a prescription wear period.

The prescription wear time will be 12-hours after the date and time the first Jewel which was applied to the subject's body transitions to Monitor Mode to the date and time that the last Jewel worn by the subject transitioned to Off Body. Periods of removal time as identified by timestamped transitions between modes, periods of removal time as attested to by a subject or health care provider and confirmed by electrocardiographic data, and periods of time in which there are missing data (e.g. due to unreturned or damaged devices) will be excluded. The prescription wear time will be calculated in hours and in days.

To calculate average hours per day, the gaps between individual device wears will be summed and the total will be subtracted from the total prescription wear time. That absolute device wear time will be divided by the total prescription wear time to obtain the average.

(Total prescription wear period – Sum of gaps between individual wears) Total prescription wear time (expressed in days)

Duration of wear for individual device wears will be recorded in minutes, calculated based off the device memory logs, and will be defined as the duration of the date and time the Jewel applied to the subject's body transitions to Monitor Mode to the time that the Jewel worn detects Off Body with the exception of the first Jewel which starts 12-hours after the first Jewel transitions to Monitor Mode.

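### SAP 5.4 takes off-body time out twice when computing average hours per day, and its prose and formula use different terms, so the 14.1 h/day compliance measure is wrong as written

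*SAP*

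**What the plan says.** SAP 5.4 sets the secondary compliance endpoint at more than 14.1 average hours per day. Prescription wear time runs from 12 hours after the first device enters Monitor Mode until the last device goes Off Body. Three things are then excluded from it. The first is given as "Periods of removal time as identified by timestamped transitions between modes". The second is off-body time that the subject or a clinician reports and the ECG record bears out. The third is time with missing data.

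For the average, "the gaps between individual device wears will be summed and the total will be subtracted from the total prescription wear time". The next sentence reads: "That absolute device wear time will be divided by the total prescription wear time to obtain the average". The displayed formula has different terms: "Total prescription wear period – Sum of gaps between individual wears) Total prescription wear time (expressed in days". The section does not define prescription wear period separately from prescription wear time.

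Individual wears run from Monitor Mode to Off Body and are "calculated based off the device memory logs".

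Related places:
- SAP 3.1 uses the same exclusion sentence to define analyzable wear time for the shock rate.
- SAP 3.2 and protocol 9.3 use an average of at least 14.1 hours a day as a per-protocol criterion.
- SAP 6 sets aside time off the device at the treating physician's direction.
- Protocol 9.4.2 leaves the compliance calculation to the SAP.

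**The concern.** The exclusion sentence suits SAP 3.1, because exposure for an event rate should count only time on the body. An hours-per-day measure is different: its denominator must contain the hours when the device was off, or non-wear cannot show. SAP 5.4 removes those hours from the total and then subtracts the gaps from what is left.

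The formula adds a second uncertainty. Its numerator and denominator carry different names, and the text does not say whether they are different quantities. Two programmers could follow the section in good faith and report very different averages for the same subject.

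Two results depend on this. One is the reported compliance figure. The other is who enters the per-protocol population. SAP 3.2 does not cite 5.4, but 5.4 is the only place that defines average hours per day, so that link is an inference.

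**Working it through.** The plan gives 14.1 h/day as a threshold without deriving it, so there is no computed figure to reproduce. The check applies the definitions as written.

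**Notation**
- S: elapsed span between the two timestamps in SAP 5.4.
- G: total gap time between wears.
- M: missing-data time.
- W = S − G − M: on-body time.
- t: true average wear in hours per day.

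**Assumptions**
- The excluded removals and the gaps are the same intervals. SAP 5.4 supports this for timestamped removals, since each wear ends at Off Body and the next starts at Monitor Mode. For attested removals, SAP 11 says that those "confirmed by electrocardiographic data will be included in the calculation of removal time".
- M = 0 unless stated.
- Ratios are multiplied by 24 to give hours per day. Hours divided by hours, as the prose alone could be read, would give a fraction (14.1/24 = 0.5875).

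**Coherent measure.** t = 24W/(W + G), so G/W = 24/t − 1.

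**Prose as written.** After the exclusions the total is T = W. The computed value is 24(T − G)/T = 24(W − G)/W = 24 − 24(24/t − 1) = 48 − 576/t.

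| True h/day (t) | 576/t | Computed h/day |
|---|---|---|
| 12 | 48.00 | 0.0 |
| 14.1 | 40.85 | 7.15 |
| 16 | 36.00 | 12.0 |
| 18 | 32.00 | 16.0 |
| 20 | 28.80 | 19.2 |
| 22 | 26.18 | 21.82 |
| 23 | 25.04 | 22.96 |

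To compute as 14.1, a subject needs 576/t = 48 − 14.1 = 33.9, so t = 576/33.9 = 16.99 h/day. Subjects with true wear from 14.1 up to 16.99 would fall on the wrong side of the threshold. The length of the prescription does not enter.

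**Displayed formula, read as a ratio**
- If *period* and *time* are synonyms, the formula is the prose calculation, with the values above.
- If *period* is the elapsed span S and *time* is the net total T, the value is 24(S − G)/T. With M = 0, S − G = W = T, so it is 24.0 for every subject, whatever the true wear.
- On that second reading, missing data push the value above 24. Assume a 90-day span less the first 12 hours, with 7 days missing and true wear of 14.1. Then S = 2,148 h, M = 168 h, G = (2,148 − 168) × (1 − 14.1/24) = 816.75 h and T = 1,163.25 h. The value is 24 × 1,331.25/1,163.25 = 27.5 h/day, which is impossible.

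**Single subtraction from an elapsed total net of missing time.** 24(S − M − G)/(S − M) returns t, so true 14.1 gives 14.1.

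**The case against.** The best defence is that the intended meaning is plain. SAP 5.4 calls the numerator absolute device wear time, which points to on-body time over elapsed time. A programmer who met an average of 0 for a subject wearing the device 12 hours a day would notice. The device is meant for continuous wear with roughly weekly exchanges, and near that pattern the double subtraction hardly matters: 22 becomes 21.82 and 23 becomes 22.96. Compliance is not formally tested (protocol 9.1), and SAP 5.1 calls the per-protocol effectiveness analysis strictly supportive.

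Most of this stands, and it limits the severity. It does not remove the error, because the intended reading requires ignoring an explicit sentence that excludes removal time. Nor can that sentence be taken to mean only physician-directed time: SAP 6 handles that separately, and 5.4 names all timestamped removals.

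A reader might go further in two directions that the documents do not support:
- **That the endpoint cannot be failed.** The constant 24.0 appears only if *period* means elapsed span and *time* means net time. The text never says so, and treating the terms as synonyms is at least as natural.
- **That the prose rule could overstate wear substantially because many removals are not gaps.** This would need a large share of off-body time to escape the gaps. The Monitor Mode to Off Body definition, and SAP 11's counting of attested removals as removal time, give little support for that.

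**Conclusion.** The concern holds. Followed as written, the prose in SAP 5.4 understates wear: 14.1 h/day computes as 7.15, and 16.99 is needed to reach 14.1. These figures assume that gaps and removals coincide and that no data are missing. They show what the rule does and do not predict what this trial would report. The displayed formula does not settle the matter, since it gives either the same understated value or 24.0, depending on an undefined term.

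The effect is confined to the descriptive secondary endpoint and, by inference, the per-protocol cut-off in SAP 3.2. A reader might infer that the shock-rate result or early stopping is compromised. They are not: SAP 3.1 defines exposure correctly for its purpose, and the interim rule in SAP 5.5 uses only the two primary endpoints. Severity is low to moderate. The definition should be corrected because it is wrong as written and cheap to put right.

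**What to change.** In SAP 5.4:

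1. Delete the removal periods from the exclusion sentence, and keep them in SAP 3.1.
2. Define one prescription wear period: the elapsed span between the two stated timestamps, less only missing-data time and the physician-directed off time already set aside in SAP 6. Take each of these out of both numerator and denominator, and do not count either as a gap.
3. Define on-body time as that period minus all other off-body time, timestamped and attested, subtracted once.
4. Compute average hours per day as on-body hours divided by that period in days.
5. Use one term in both prose and formula.
6. State that the 14.1 h/day criterion in SAP 3.2 uses this quantity.

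The cost is SAP wording and one derived variable. The inputs are the device logs, plus the attestation and physician-direction records on which the SAP already relies. Sample size, visits and the primary analyses do not change.
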